10.4.4 Other safety variables

10.4.4.1 Assessment and management of TB and TB risk factors

A summary of the number and percentage of subjects with negative, positive, and indeterminate IGRA (Interferon-Gamma Release Assay) results at all applicable visits will be presented for the entire study.

A by-subject listing of the “Evaluation of signs and symptoms of tuberculosis” questionnaire data and IGRA results will be provided.

A by-subject listing of the result of chest x-ray for tuberculosis will be provided by treatment.

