8.3.11 Week 52 (± 7 days)

The following procedures or assessments will be performed/recorded prior to administration of the IMP:

- Obtain informed consent for the open-label study

- Vital signs (sitting systolic and diastolic BP, pulse rate, and body temperature) should be obtained prior to blood sampling
- Obtain blood and urine samples for the following analyses prior to dosing:
 - Urine pregnancy test
 - IGRA tuberculosis test; it is recommended that the QuantiFERON TB test be performed
- PASI
- Percentage of BSA
- IGA
- PHQ-9
- eC-SSRS
- Concomitant medications
- Record AEs
- Contact the IRT

After completion of the above-mentioned procedures, administration of bimekizumab or placebo will occur.

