8.4 Premature End of Treatment Visit

If a subject is withdrawn from the study:

- The subject will be withdrawn from IMP, will undergo the same assessments as the Week 56 visit (see [Section 8.3.12](#)), and will enter the SFU Period.
- The subject will be encouraged to return for the SFU Visit (20 weeks after the last received dose; see [Section 8.5](#)).

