12.3.1.1 Tuberculosis assessment by IGRA

During conduct of the study, the TB assessment by IGRA (QuantiFERON TB test is recommended) will be performed as described in [Table 5–1](#) for all subjects. The test results will be reported as positive, negative, or indeterminate. Positive and indeterminate TB test results must be reported as an AE and appropriately updated once the final diagnosis is known (e.g. active TB, latent TB, or false positive TB test). UCB also recommends that a TB specialist be consulted where TB (latent or active) is suspected or if there are doubts regarding test results. If latent or active TB is identified, subject must undergo appropriate study-specified withdrawal procedures. The retest during Screening must be done during the protocol-defined Screening window.

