3.6 Treatment assignment and treatment groups

It is expected that subjects receive treatment as randomized and hence safety analyses will be based on the SS, as randomized. However, if after unblinding it is determined that subjects randomized to a treatment arm had never received such treatment, then for safety analyses, these subjects will be reallocated to the appropriate received treatment groups, unless otherwise specified.

Efficacy analyses should be performed according to randomized treatment and not actual treatment received.

Summaries based on SS or RS will be provided by “BKZ 320mg Q4W”, “BKZ 320mg Q4W/Q8W”, “BKZ Total” and “ADA” treatment groups. The ADA group will only be presented from Baseline to Week 24 in the by-visit summaries.

Summaries based on BKZ Week 24 set will be provided by “BKZ 320mg Q4W”, “BKZ 320mg Q4W/Q8W” and “ADA/BKZ 320mg Q4W” treatment groups for disposition, baseline assessments and efficacy. The ADA/BKZ 320mg Q4W group will be presented from Week 28 to Week 56 in the by-visit summaries for the PASI scores and the DLQI only.

For safety, summaries on the BKZ set will be provided by “BKZ 320mg Q4W”, “BKZ 320mg Q8W” and “BKZ Total”. BKZ Q4W will include data from subjects in the BKZ Q4W/Q8W arm (up to Week 16) and the ADA/BKZ Q4W arm (after Week 24).

Safety summaries on the BKZ Week 24 set will be provided for subjects switching from Adalimumab to Bimekizumab.

Summaries based on the Maintenance set will be provided by “BZK 320mg Q4W”, “BKZ 320mg Q4W/Q8W” and “BKZ Total”.

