10.2 Adverse events

An AE is any untoward medical occurrence in a subject or clinical investigation subject administered a pharmaceutical product that does not necessarily have a causal relationship with this treatment. An AE can therefore be any unfavorable and unintended sign (including an abnormal laboratory finding), symptom, or disease temporally associated with the use of a medicinal (investigational) product, whether or not related to the medicinal (investigational) product.

Adverse events will be coded according to the Medical Dictionary for Regulatory Activities (MedDRA version 19.0). For subjects who switch treatment during the study i.e. those randomized to BKZ Q4W/Q8W or ADA/BKZ, any adverse events that occur after initiation of the new treatment are attributable to the new treatment. If an adverse event occurs on the date of a treatment switch, the event is attributed to the original treatment. The only exception to this is if the AE fulfills the criteria for an anaphylactic reaction as defined in the bimekizumab safety topics of interest document. Specifically, this includes the following:

- Events that fulfill the anaphylaxis criteria for acute events (refer to Appendix A in section 12)
- Events with a reported term containing the term “hypersensitivity (SMQ)”
- Events with an HLT of “Administration site reactions NEC”
- Events with an HLT of “Injection site reactions”

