where N_{AE} is the total number of AEs, T_{Risk} is the time at risk for each subject, and N is the total number of subjects at risk.

No confidence interval will be computed for EAER.

Selected summaries for the subjects who switch from adalimumab to bimekizumab will be presented by time of onset (≤ 70 days or > 70 days from the final dose of adalimumab). Only events starting after the first dose of bimekizumab will be included.

70 days was chosen as it is approximately equal to five half lives of adalimumab.

Selected summaries, as specified in Section 10.2.2, will include the risk difference between bimekizumab and adalimumab. The risk difference is calculated as:

$$RD = IP_{BKZ} - IP_{ADA}$$

where IP_{BKZ} is the incidence proportion for the bimekizumab-treated group and IP_{ADA} is the incidence proportion for the adalimumab group. Note that incidence proportion simply refers to the percentage of subjects within the specified treatment group that experienced a given adverse event.

The standard error for the risk difference is calculated as follows:

$$SE_{RD} = \sqrt{\left(IP_{BKZ} \times \left(\frac{1 - IP_{BKZ}}{n_{BKZ}} \right) \right) + \left(IP_{ADA} \times \left(\frac{1 - IP_{ADA}}{n_{ADA}} \right) \right)}$$

where n_{BKZ} is the number of subjects in the bimekizumab-treated group and n_{ADA} is the number of subjects in the adalimumab group.

The corresponding confidence interval for the risk difference is as follows:

$$CI_{RD} = RD \pm Z_{1-\alpha/2} \times (SE_{RD})$$

where $Z_{1-\alpha/2}$ is the Z statistic for the corresponding level of alpha. For the risk difference confidence intervals calculated in this SAP, 1.96 will be used (corresponding to a two-sided alpha of 0.05 and 95% confidence interval). Risk difference and the corresponding confidence interval will be presented as a percentage.

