10.2.2 AE summaries

The following summaries will be provided in five different ways: through Week 24 for the SS, through initial and maintenance treatment period for the BKZ Set, through initial treatment period for the SS, through the maintenance period for the MS (excluding patients randomized to ADA) and from Week 24 to Week 56 for the BKZ Week 24 Set for patients randomized to ADA switching to BKZ (to examine the events occurring within 70 days and >70 days of the treatment switch).

- Incidence of TEAEs – Overview
- Incidence of TEAEs per 100 subject years by SOC, HLT, and PT
- Incidence of Serious TEAEs per 100 subject years by SOC, HLT, and PT

The following summary will be provided in four different ways: through Week 24 for the SS, through initial and maintenance treatment period for the BKZ Set, through initial treatment period for the SS and through the maintenance period for the MS (excluding patients randomized to ADA).

- Incidence of TEAEs Leading to Discontinuation per 100 subject years by SOC, HLT, and PT

The following summaries will be provided in two different ways: through Week 24 for the SS, and through initial and maintenance treatment period for the BKZ Set:

- Incidence of TEAEs Leading to Death by SOC, HLT, and PT
- Incidence of TEAEs by Maximum Relationship by SOC, HLT, and PT
- Incidence of Serious TEAEs by Relationship SOC, HLT, and PT – Note: For EudraCT reporting purposes
- Incidence of Related Serious TEAEs by SOC, HLT, and PT
- Incidence of TEAEs Leading to Death by Relationship by SOC, HLT, and PT – Note: For EudraCT reporting purposes
- Incidence of TEAEs by Maximum Severity, SOC, HLT, and PT
- Incidence of TEAEs by decreasing frequency of PT
- Incidence of TEAEs Above Reporting Threshold of 5% by SOC and PT
- Incidence of Non-Serious TEAEs by SOC, HLT, and PT
- Incidence of Non-Serious TEAEs by Relationship SOC, HLT, and PT
- Incidence of Non-Serious TEAEs Above Reporting Threshold of 5% by SOC and PT
- Incidence of Non-Serious TEAEs Above Reporting Threshold of 5% by Relationship SOC and PT
- Incidence of Related TEAEs by SOC, HLT, and PT
- Incidence of Related TEAEs Above Reporting Threshold of 5% by SOC and PT

The following summary will be provided through Week 24 for the SS:

- Incidence of TEAEs Above Reporting Threshold of 5% with Risk Differences by SOC and PT
- Incidence of Serious TEAEs and Risk Differences by SOC and PT

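### Week 52 IGRA conversions in the adalimumab arm would be shown as bimekizumab events more than 70 days after adalimumab, although their onset is known only to lie after Screening

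*SAP*

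**What the plan says.** The test appears in two visit lists only: Screening (Protocol 8.1) and Week 52 (Protocol 8.3.11), the latter reading "IGRA tuberculosis test; it is recommended that the QuantiFERON TB test be performed". A subject who leaves early "will undergo the same assessments as the Week 56 visit" (Protocol 8.4), and the Week 56 list in Protocol 8.3.12 contains no IGRA. Protocol 12.3.1.1 adds: "Positive and indeterminate TB test results must be reported as an AE and appropriately updated once the final diagnosis is known".

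SAP 10.2.1 classes an AE as treatment-emergent by its start date. For subjects who change regimen, SAP 10.2 says that "any adverse events that occur after initiation of the new treatment are attributable to the new treatment". SAP 10.2.1 continues: "Selected summaries for the subjects who switch from adalimumab to bimekizumab will be presented by time of onset", cut at 70 days from the final adalimumab dose. SAP 10.2.2 schedules that output "from Week 24 to Week 56 for the BKZ Week 24 Set for patients randomized to ADA switching to BKZ". In the BKZ Set safety tables, SAP 3.6 groups by regimen: the BKZ Q4W column takes the adalimumab arm after Week 24 and the Q4W/Q8W arm up to Week 16.

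For IGRA itself, SAP 10.4.4.1 plans "A summary of the number and percentage of subjects with negative, positive, and indeterminate IGRA (Interferon-Gamma Release Assay) results at all applicable visits" over the whole study, plus a by-subject listing. It names no columns and does not tabulate conversions. SAP 3.6 shows the ADA group only to Week 24 in by-visit summaries.

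**The concern.** A conversion without symptoms is dated by when someone looks. In the adalimumab arm the scheduled look comes 28 weeks after the switch, with no scheduled test at the switch itself. The infection may have been acquired during the 24 weeks on adalimumab, but the AE would be entered at Week 52 and counted to bimekizumab.

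The 70-day split exists to separate events that could be adalimumab carry-over from later ones. For this event it cannot do so, and it gives a definite period to an onset that is not known. TB is a pre-specified safety topic (Protocol 12.1.1.4), and Protocol 2.1.2 notes boxed warnings for serious infection with TNF inhibitors. Unless a test was prompted earlier, a reader of the tables would see no conversions on adalimumab and all of that arm's conversions on bimekizumab after washout.

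**Working it through.** **The plan's own figure.** The cut is 70 days, described in SAP 10.2.1 as about five adalimumab half-lives. That implies 70/5 = 14 days per half-life. The documents give no half-life, so the figure cannot be checked, and nothing below depends on it.

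**Position of the Week 52 test.** The last adalimumab dose is Week 23 and the first bimekizumab dose is Week 24 (Protocol 7.2). Windows are ±3 days to Week 24 and ±7 days from Week 28 (Protocol 8).
- From last adalimumab dose: (52 − 23) × 7 = 203 days, range 203 ± 10 = 193 to 213.
- From first bimekizumab dose: (52 − 24) × 7 = 196 days, range 186 to 206.

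Every scheduled Week 52 test in this arm is therefore on bimekizumab and well beyond day 70.

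**Share of the between-test interval spent on adalimumab.** Screening is 2 to 5 weeks before first dose, so the interval is 54 to 57 weeks: 24/54 = 44% and 24/57 = 42%. If the conversion rate on adalimumab is r times the rate in the remaining weeks, the share of conversions arising on adalimumab is 24r/(24r + 28 + s), where s is the number of Screening weeks:

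| r (assumed) | s = 2 | s = 5 |
|---|---|---|
| 0.5 | 12/42 = 29% | 12/45 = 27% |
| 1 | 24/54 = 44% | 24/57 = 42% |
| 2 | 48/78 = 62% | 48/81 = 59% |

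**Effect on rates (illustration).** Assume 150 per arm, one equal constant conversion rate L, no conversions before first dose, all detection at Week 52, AE onset at the test date and follow-up to Week 56. Observed rate over true rate, per subject in each arm:
- ADA through Week 24: 0/24 = 0.
- Switch arm, Week 24 to 56: 52/32 = 1.6.
- BKZ Set, Q4W column: (52 + 52)/(56 + 16 + 32) = 104/104 = 1.00.
- BKZ Set, Q8W column: 52/40 = 1.30. Ratio to Q4W: 1.30.
- Maintenance Set, Q4W and Q4W/Q8W: 52/40 = 1.30 in each. Ratio: 1.00.

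The Maintenance Set table overstates both rates by the same factor, so its comparison is fair. The Q4W versus Q8W distortion occurs only where the BKZ Set is split by regimen.

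**Number of subjects.** The documents give no conversion rate. At an assumed 0.5 to 3 per 100 subject-years, positives in the adalimumab arm from first dose to Week 52 are 150 × [1 − exp(−rate × 364/365.25)] = 0.75 to 4.42. At r = 1, 24/52 of these arose on adalimumab: 0.34 to 2.04.

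**Where the IGRA results would appear.** Under the SS default, the columns of the 10.4.4.1 table are the randomized arms. SAP 3.6 ends the ADA by-visit column at Week 24, before that arm's only scheduled on-treatment IGRA. Its Week 52 results have no stated place.

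**The case against.** A reader might infer that no planned table follows the randomized sequence. That is not so. SAP 10.2.2 plans the main TEAE tables for the maintenance period in the Maintenance Set without the adalimumab arm, and SAP 3.6 gives its columns as BKZ Q4W, BKZ Q4W/Q8W and BKZ Total. The BKZ Week 24 Set table isolates the switch arm. Week 52 IGRA events can be read by randomized arm across these two, and the first removes the 1.30 ratio. This part of the objection stands. Neither table helps with adalimumab attribution, however: the first excludes that arm and the second is the one carrying the 70-day split.

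No document says that the AE start date is the test date. The investigator records it, the AE is updated after diagnosis, and Protocol 14.5.1 allocates by the day the event occurred. This also stands. The test date is the natural entry for a laboratory finding without symptoms, and the absence of a rule is part of the gap.

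TB surveillance on adalimumab is more than two blood tests. The questionnaire and a TB-directed examination are done at Weeks 12 and 24, a positive answer prompts further assessment, and TB also passes through the opportunistic-infection review, whose listing shows onset dates. Some conversions could therefore be dated earlier. A silent conversion without recognised exposure would not be.

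Finally, attribution by treatment at onset is a general rule, the split makes no causal claim, and a special rule for one AE type is partly a matter of taste. That is fair, and it limits the severity of the point.

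**Conclusion.** The concern holds in a limited form, as a minor point. If the start date is the test date, every scheduled-test conversion in the adalimumab arm is counted to bimekizumab and shown beyond 70 days (day 203, range 193 to 213), although 42% to 44% of the between-test interval was adalimumab time. No planned table corrects this. Separately, SAP 10.4.4.1 gives result counts rather than conversions and leaves the adalimumab arm's Week 52 results without a stated column.

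The documents do not support the stronger inference that the Q4W versus Q8W safety comparison is distorted throughout. The 1.30 ratio belongs to the BKZ Set by-regimen table and rests on an equal constant rate. Nor do they establish how many conversions would arise on adalimumab; the 0.34 to 2.04 subjects above depend on assumed rates. The illustration also takes follow-up to Week 56, although converters must stop IMP (Protocol 12.3.1). Efficacy results and patient management are unaffected.

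**What to change.** In SAP 10.4.4.1, add a Screening-to-post-baseline IGRA table with columns BKZ Q4W, BKZ Q4W/Q8W, ADA/BKZ Q4W and total. Define conversion as negative at Screening and positive at any later test, unscheduled tests included, among subjects who were retested, and show how many were. Give entry positives, entry indeterminates and later indeterminates their own rows. Treated latent-TB subjects may enrol (Protocol 6.2, criterion 12), so a Week 52 positive need not be a conversion.

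In SAP 10.2.1, state that a TEAE consisting only of an IGRA result has an onset between the last negative test and the test date. Where the last negative test precedes the treatment switch, show the event as 'onset not determinable' in the 70-day switch table. In the BKZ Set by-regimen table, add a footnote that refers to the by-sequence table.

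The cost is SAP wording, one extra table and a special-case rule for one AE type. All data are already collected, so no visits or samples are added.

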10.4.4.2 Electronic Columbia Suicide Severity Rating Scale (eC-SSRS)

eC-SSRS questionnaire will be self-administered by the subject and assessed by trained study personnel. This scale will be used to assess suicidal ideation and behavior that may occur during the study. Results of the eC-SSRS will be summarized using the number of subject and percentage with (i) events in suicide behavior, (ii) suicidal ideation, (iii) suicidal behavior and ideation, and (iv) self-injurious behavior without suicidal intent.

Suicidal ideation is defined as an event in any of the following 5 categories:

- Wish to be dead
- Non-specific active suicidal thoughts
- Active suicidal ideation with any methods (not plan), without intent to act
- Active suicidal ideation with some intent to act, without specific plan
- Active suicidal ideation with specific plan and intent

Suicidal behavior is defined as an event in any of the following 4 categories:

- Actual attempt
- Interrupted attempt
- Aborted attempt
- Preparatory acts or behavior

Suicidal behavior or ideation is defined as an event in any of the above 9 categories.

Self-injurious behavior without suicidal intent is defined as an event in the category non-suicidal self-injurious injuries.

The incidence of subjects with suicidal ideation, suicidal behavior, suicidal ideation or behavior, and self-injurious behavior will be summarized by treatment group through week 24 and through initial and maintenance treatment period.

A by-subject listing of the eC-SSRS questionnaire data will be provided by treatment group.

10.4.4.3 Pregnancy testing

Pregnancy testing will consist of serum testing at the Screening. The pregnancy test will be urine at all other visits.

A by-subject listing of the pregnancy test data will be provided by treatment group.

10.4.4.4 Childbearing potential and Lifestyle

Childbearing potential and lifestyle will be collected at Screening. A by-subject listing will be provided for all the subjects screened.

10.4.5 Patient Health Questionnaire 9 (PHQ-9)

The PHQ-9 is a multipurpose instrument for screening, diagnosing, monitoring, and measuring the severity of depression. The PHQ-9 scores for depression range from 0 to 27 with higher scores indicating worse state. A score of 5-9 is considered to be minimal symptoms of depression. If any of the 9 questions are missing, then the score is treated as missing. A score of 10 to 14 is considered minor depression, dysthymia, or mild major depression. A score of 15 to 19 is considered to indicate moderately severe major depression, and a score ≥ 20 is considered to be severe major depression.

MI-MCMC/monotone regression method will be used to impute missing data. If the imputation model cannot converge, last observation carried forward (LOCF) will be used.

Change from Baseline in PHQ-9 is derived as post-Baseline score minus Baseline score. It will be summarized by treatment group through initial and maintenance treatment period for the SS and for the BKZ Week 24 Set for subjects switching from adalimumab to bimekizumab.

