3.3 Other objectives

The other objectives of the study are to demonstrate the effects of bimekizumab on aspects of the disease:

- Assess the maintenance of efficacy of bimekizumab dosing Q4W versus Q8W during the Maintenance Treatment Period
- Assess the efficacy of bimekizumab over time
- Assess the change of skin-related quality of life (QOL)
- Assess the change of general health-related QOL
- Assess the change in nail PSO over time in subjects with nail PSO at Baseline
- Assess the change in scalp PSO over time in subjects with scalp PSO at Baseline
- Assess the change in palmoplantar PSO over time in subjects with palmoplantar PSO at Baseline
- Assess the symptoms of PsA as measured by the Psoriatic Arthritis Screening and Evaluation (PASE) questionnaire
- Assess the change of patient-reported joint symptoms in subjects with PsA at Baseline
- Assess the change in symptoms of PSO as reported by subjects using the Patient Symptom Diary (all items) through Week 24
- Assess depression
- Assess the PK of bimekizumab

- Assess the immunogenicity of bimekizumab
- Assess work productivity
- Assess the effect of bimekizumab on gene and protein expression, and explore the relationship between genomic, genetic, and proteomic biomarkers and disease biology, drug treatment and inflammatory and immune responses (from consenting subjects who agree to participate in the biomarker substudy)
- Assess the safety and tolerability of bimekizumab

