- Change from Baseline in the PASE questionnaire scores (function score, symptom score, and total score)
- Shift from Baseline in PASE score suggestive of PsA (<47 versus ≥47)

- Change from Baseline in Short Form 36-item Health Survey (SF-36) Physical Component Summary (PCS) score, and Mental Component Summary (MCS) score, and individual domains
- Responses to Euro-Quality of Life 5-Dimensions, 3 levels (EQ-5D-3L), absolute and changes from Baseline in EQ-5D-3L VAS scores
- Change from baseline in Patient Health Questionnaire-9 (PHQ-9) scores
- Change from Baseline in Work Productivity and Activity Impairment Questionnaire-specific health problem (WPAI-SHP) V2.0 adapted to PSO scores

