 - Suicidal ideation in the past month prior to the Screening Visit as indicated by a positive response (“Yes”) to either Question 4 or Question 5 of the “Screening” version of the eC-SSRS.
- 27a. Subject has presence of moderately severe major depression or severe major depression, indicated by a score of ≥ 15 using the screening PHQ-9. Medication used to treat depression should be stable for 8 weeks prior to Baseline.
28. Subject is a member of Investigator site personnel directly affiliated with this study and/or their immediate families. Immediate family is defined as a spouse, parent, child, or sibling, whether biological or legally adopted.
29. Subject is a UCB employee or employee of third-party organizations involved in the study.
30. Subject is taking or has taken prohibited psoriasis medications without meeting the mandatory washout period relative to the Baseline Visit (Table 7–2).

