- Active suicidal ideation as indicated by a positive response ("Yes") to Question 5 of the "Since Last Visit" version of the eC-SSRS
- Any suicidal behavior since last visit.
- Severe major depression as indicated by a PHQ-9 score ≥ 20 .

The mental health consultation must be recorded in source documentation.

Investigators should attempt to obtain information on subjects in the case of withdrawal or discontinuation. For subjects considered as lost to follow-up, the Investigator should make an effort (at least 1 phone call and 1 written message to the subject), and document his/her effort (date and summary of the phone call and copy of the written message in the source documents), to complete the final evaluation. All results of these evaluations and observations, together with a narrative description of the reason(s) for removing the subject, must be recorded in the source documents. The electronic Case Report Form (eCRF) must document the primary reason for withdrawal or discontinuation.

Investigators should contact the Medical Monitor, whenever possible, to discuss the withdrawal of a subject in advance.

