12.1.1.4 Other safety topics of interest

Pre-specified safety topics of interest for the study are: infections (serious, opportunistic, fungal, and TB), neutropenia, hypersensitivity, suicidal ideation and behavior, depression, major cardiovascular events, liver function test changes/enzyme elevations, malignancies, and inflammatory bowel diseases (with gastroenterology referral, as appropriate). This is based on findings from the IMP clinical program to date, potential risks generally associated with biologic immunomodulators, or findings from other medicines with a related mechanism of action. There are no specific AE reporting requirements for these topics, however special monitoring, additional data collection activities, and/or enhanced signal detection activities (within UCB) are in place.

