2.2.3.2 Other safety variables

Safety variables to be assessed are:

- Severity and frequency of AEs (including serious AEs)
- Change from Baseline in vital signs
- ECG results
- Change from Baseline in clinical laboratory values (chemistry, hematology)
- Change from baseline in Patient Health Questionnaire (PHQ)-9 scores

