- Minimum and maximum will have the same number of decimal places as the original value.

Derived variables in general will display the mean, SD and median to 1 more decimal place than the variables used in the derivation. If the number of decimal places reported in the raw data is varied then use either the maximum raw number of reported decimal places or 3, whichever is the lowest, as a guide for the descriptive statistics.

Statistical tests of efficacy variables will be presented as two-sided p-values rounded to three decimal places. P-values less than 0.001 will be presented as “<0.001” and p-values greater than 0.999 will be presented as “>0.999.” Statistical comparisons will be two-sided and will be performed at the 0.05 level of significance.

A complete set of data listings containing all documented data as well as calculated data (e.g. change from Baseline) will be generated.

Per protocol, visit windows of ± 3 days from the first dose to Week 24 and ± 7 days from Week 28 to Week 56 are permissible. For the SFU Visit, visit window is ± 7 days from final dose. All by-visit summaries will contain nominal (i.e. scheduled) visits only. Unscheduled visits will not be mapped to scheduled visits except for some assessments that may occur within a 3-day time window of a scheduled visit. In that case, the assessment will be mapped to the corresponding scheduled visit and will be used for the analysis. This will only occur for some vendor data.

For missing PASI and IGA assessments at Week 16, available data from all visits (unscheduled or scheduled but without a planned assessment) within the 3 days window will be included.

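### PHQ-9 is summarized only as imputed change from Baseline: the SAP counts no subjects reaching its severity bands and gives depression no safety-topic output

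*SAP*

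**What the plan says.** Protocol 3.3 lists "Assess depression" among the other objectives. The only PHQ-9 variable attached to it is "Change from baseline in Patient Health Questionnaire-9 (PHQ-9) scores" (Protocol 4.3.1, as an efficacy variable). The SAP keeps the same variable, "Change from baseline in Patient Health Questionnaire (PHQ)-9 scores", but places it under safety (SAP 2.2.3.2), and SAP 3.10 discloses that move.

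SAP 10.4.5 describes the score bands (10 to 14, 15 to 19, 20 or more). It then plans change from Baseline by treatment group and states that the "MI-MCMC/monotone regression method will be used to impute missing data", with LOCF as the backup. It plans no band count, threshold count or shift table.

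Protocol 12.1.1.4 puts depression among the pre-specified safety topics ("suicidal ideation and behavior, depression, major cardiovascular events"). Protocol 14.5.1 says these topics will be summarized, with detail in the SAP.

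Two thresholds frame the scores. Exclusion criterion 27a reads "Subject has presence of moderately severe major depression or severe major depression, indicated by a score of" 15 or more at Screening. Withdrawal criterion 13 includes "Severe major depression as indicated by a PHQ-9 score" of 20 or more. Criterion 12 adds referral and possible withdrawal at 15 to 19 with a 3-point rise.

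On visits, SAP 3.1 says: "All by-visit summaries will contain nominal (i.e. scheduled) visits only".

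**The concern.** A safety question about depression is a question about individuals: how many subjects in each arm became clinically depressed? The plan answers with a mean. The mean can improve as skin clears while a few subjects worsen severely, and nothing planned for PHQ-9 would count those few. The dedicated topic outputs would not count them either, because depression has none. A reader of the study report could then see a neutral or favourable PHQ-9 table with no rate, by arm, of new moderately severe or severe scores. The bands needed for that rate are already written into the SAP.

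**Working it through.** The documents give no PHQ-9 mean, SD, correlation or event rate, so there is no plan figure to reproduce. Steps 1 to 3 compare text; steps 4 to 6 illustrate size on stated assumptions.

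**1. Topic coverage.** Protocol 12.1.1.4 names infections, neutropenia, hypersensitivity, suicidal ideation and behavior, depression, major cardiovascular events, liver changes, malignancies and inflammatory bowel disease. SAP 10.2.3 has an entry for each of these except depression. Its neuropsychiatric entry covers adjudicated suicidal ideation and behavior only. SAP 3.10 does not mention the gap.

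**2. Handling compared with other quantitative safety data.**

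| Data | Threshold or outlier counts | Missing values |
|---|---|---|
| Laboratory (SAP 10.3) | Yes, plus shift tables that use unscheduled visits | Observed cases |
| Blood pressure (SAP 10.4.1) | Yes | No imputation specified |
| ECG (SAP 10.4.3) | Yes | No imputation specified |
| PHQ-9 (SAP 10.4.5) | No | Multiple imputation, LOCF backup |

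**3. Scores that by-visit tables can lose.** SAP 3.1 generally leaves out unscheduled scores. SAP 3.3 moves a withdrawal (PEOT) visit falling between scheduled visits to the next scheduled visit, and drops the value from by-visit tables if the assessment is not planned there. By Protocol 8.2 and 8.3, the post-Baseline visits through Week 24 are Weeks 1, 3, 4, 5, 7, 8, 9, 11, 12, 13, 15, 16, 17, 19, 20, 21, 23 and 24, which is 18 visits. PHQ-9 is planned at 6 of them (Weeks 4, 8, 12, 16, 20, 24), so 12 of 18 have none. A PEOT score taken after the Week 4 visit and before Week 5 maps to Week 5 and leaves the table; later visits are then imputed. From Week 28 to Week 56 every scheduled visit includes PHQ-9, so this loss arises only up to Week 24.

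**4. What a mean shows.** Shift = k × (20 − 5)/N; standard error = SD/√N. Assumed: a rise from 5 to 20, and SD 4 to 5.
- k = 3, N = 150 (2%): 3 × 15/150 = 0.30 points. Standard error = 4/√150 = 0.33 to 5/√150 = 0.41. (At SD 3 it is 0.24, and 0.30 exceeds it.)
- k = 5, N = 150 (3.3%): 5 × 15/150 = 0.50 points.
- The 95% half-width for a mean difference, 150 versus 300, is 1.96 × SD × √(1/150 + 1/300) = 0.196 × SD, which is 0.59, 0.78 and 0.98 at SD 3, 4 and 5. Both shifts lie inside it.
- If everyone else improves by 1 point, the net mean change is 0.02 × 15 − 0.98 × 1 = −0.68 with 2% worsening, and 0.05 × 15 − 0.95 × 1 = −0.20 with 5% worsening. Both read as improvement.

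**5. What imputation does.** For a subject whose last observed score is 20, the expected next imputed score is μ + r(20 − μ). With assumed μ of 2 to 3 and correlation r of 0.5 to 0.9, this runs from 2 + 0.5 × 18 = 11.0 to 3 + 0.9 × 17 = 18.3. Three visits later, if correlation decays as r³, it runs from 4.2 to 15.4. The observed 20 stays; later visits drift toward the arm's level.

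**6. What a count shows.** At a true rate of 2%, the chance of at least one case is 1 − 0.98¹⁵⁰ = 95% in an arm of 150 and 1 − 0.98³⁰⁰ = 99.8% in 300.

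**The case against.** Much of the case on the other side stands.

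- A reader might infer that mean PHQ-9 change is the sole answer to the depression objective. It is not. SAP 10.2.2 tabulates adverse events, and those leading to discontinuation, by SOC, HLT and PT. SAP 5.1 summarizes discontinuation reasons, eC-SSRS and adjudicated suicidality have their own outputs, and all data are listed.
- A reader might infer that severe cases are erased by imputation. They are not. Only missing values are filled, using the subject's own earlier scores, and a crossing score at a scheduled PHQ-9 visit remains. The planned maximum, averaged over imputations, cannot fall below the largest observed change, so a rise from 5 to 20 at such a visit would show as at least +15.
- A reader might carry over the full-adherence estimand of SAP 8.1.3.1. That text concerns a sensitivity analysis of the co-primary endpoints; the SAP does not say it of PHQ-9.
- A reader might see the entry and withdrawal thresholds as hiding the outcome. The entry rule is the same for every arm, still admits scores of 10 to 14, and makes most later scores of 15 or more new, hence easy to interpret.
- The protocol promises no PHQ-9 band table, and small counts are imprecise: 3 of 150 has an exact 95% interval of 0.4% to 5.7%, and 3 of 150 against 0 of 150 gives Fisher p = 0.25.

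These points limit the concern without closing it. A maximum does not say how many subjects worsened. Adverse event tables depend on an event being reported: Protocol 12.1.1.4 sets no specific adverse event reporting requirement for these topics, and withdrawal criteria 12 and 13 call for referral and a source record, not an adverse event entry. PHQ-9 is the systematically collected measure, and its threshold crossings go uncounted. Protocol 14.5.1 does say that the topics, depression included, will be summarized.

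**Conclusion.** The point holds as a reporting gap in safety. PHQ-9 is summarized only as change from Baseline with multiple imputation; no count of subjects reaching the recited bands is planned; and depression alone among the protocol's safety topics lacks an output in SAP 10.2.3, with no disclosure in SAP 3.10. Some unscheduled and early PEOT scores also fall out of the by-visit tables.

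The documents do not support saying that depression would go unreported or that severe scores would be overwritten. The size given (0.3 points for 3 of 150, against a standard error of 0.33 to 0.41) rests on an assumed event rate, an assumed rise and an assumed SD of 4 to 5. It shows that a mean is insensitive to a few severe cases, not that such cases will occur. Whether the SAP 4.2.1 rule that sets efficacy data to missing 35 days after the last treatment applies to PHQ-9, now labelled safety, is unclear. The primary efficacy conclusions are untouched.

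**What to change.** In SAP 10.4.5, add two observed-data summaries that include unscheduled and PEOT scores:
- worst post-Baseline PHQ-9 band by Baseline band;
- number and percentage of subjects with any post-Baseline score of 10 or more, 15 or more, and 20 or more.

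Present both by arm for the SS through Week 24 and for the BKZ Set through Week 56. For subjects switching from adalimumab, state which Baseline applies, since SAP 3.2 does not give PHQ-9 a bimekizumab Baseline; SAP 10.3 uses the last value before the switch for laboratory shift tables.

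Report PHQ-9 change on observed values, with the imputed version as supportive. Add a depression adverse event table to SAP 10.2.3 so that it matches Protocol 12.1.1.4 and 14.5.1.

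The cost is two or three more tables from data already collected, with counts too small for firm comparison between arms. No withdrawal or other clinical rule changes.
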